### **II. GOALS/AIMS**

The overarching aim of the proposal is to evaluate ways to enhance quit line treatment for low-income smokers in terms of abstinence, costs, and reach. The specific aims of the project are listed below.

1. To assess the main and interactive effects of the four experimental factors (see below) on biochemically confirmed, 7-day point-prevalence abstinence at 6-month follow-up among low-education, uninsured, or Medicaid-eligible smokers who relapse following a standard WTQL intervention. Secondary abstinence outcomes are self-reported point-prevalence abstinence 12-weeks post-quit and continuous abstinence between months 1 and 6 post-quit.

Factors	Levels
1. Quit line counseling intensity	1. 1 vs. 4 proactive counseling calls
2. Nicotine replacement therapy (NRT) intensity	2. Patch (2 wks) vs. Patch+ Lozenge (4 wks)
3. SmokefreeTXT text messages	3. Proactive enrollment vs. none
4. Financial incentives for treatment engagement	4. \$30-\$150 vs. none
2. To evaluate the cost-effectiveness of each intervention component overall and in the context of the other components (i.e., additive and interactive effects and their impact on cost-effectiveness). The aim is to develop data to inform future quit line care planning and policy.	
3. To identify demographic and smoking history moderators of treatment engagement and response and mediators of intervention effects (e.g., treatment engagement) on 6-month abstinence. This aim will identify sub-populations that may not benefit equally from enhanced WTQL services and will suggest ways to refine the treatments to enhance their efficacy.	

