## G. Detailed study procedures: recruitment and retention

Personnel from three organizations will have contact with study participants or their data. Staff at Optum, operator of the WTQL, will recruit, screen, consent, assess, randomize, and deliver treatment to participants. Personnel from ICF International, the operator of SmokefreeTXT, will not have direct contact with participants, since SmokefreeTXT is a fully automated texting program. Personnel at ICF International will, however, transmit participant data on use of SmokefreeTXT, cell phone numbers, and basic demographics. Finally, UW-CTRI personnel will interact with participants to conduct follow-up telephone interviews (12- and 26-weeks post-quit

day) and to collect biochemical saliva samples via mail, collect breath carbon monoxide (CO) test results via email, or biochemically verify abstinence at brief in-person visits at UW-CTRI offices (26-weeks post-quit day) among some or all of the participants who claim they have not smoked in the last 7 days at the 26-week follow-up interview. The table below details the activities that participants will complete during the study and identifies the entity responsible for implementation. Coordination of all activities will be led by UW-CTRI and UW-CTRI will perform all data analyses.

As shown below, recruitment will be conducted by designated staff at the WTQL by inviting the subset of registered quit line callers meeting study eligibility prerequisites to screen for a study evaluating program enhancements for smokers who want to quit within 2 weeks. Staff at UW-CTRI will communicate with the WTQL team working on this project at least monthly to monitor progress in recruitment, treatment engagement (i.e., retention), and implementation challenges. To promote recruitment, WTQL staff will make at least 5 attempts to reach prospective enrollees. Similarly, to promote retention, WTQL Quit Coaches will make at least 5 attempts to schedule/deliver each counseling session by telephone. Letters will be sent to individuals meeting study prerequisites to encourage them to reconnect with the WTQL. Staff at the WTQL will be responsible for processing incentive payments to participants as soon as possible after they are earned. Staff at the WTQL will also be responsible for assessing adverse events related to its interventions in accordance with their existing protocols (i.e., staff physician review).

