Collect Baseline Data (Attach- ment F)	
 
• Socioeconomic indicators (income, employment)
 
• Cessation history
 
• Recent nicotine & e-cig product use and costs
 
• Past 6-mo healthcare use
 
• Frequency of text messaging
 
• Psychiatric history
 
• Perceived stress
 
• Menthol use
 
• Indicators of relapse proneness (e.g., exposure to others smoking, craving when abstinent)
 
• Use and costs of stop-smoking treatments since last QL call
 
• 1-3 collateral names & phone numbers
 
	WTQL
Initiate Treatment	
 
• Randomize to treatment
 
• Schedule first/only WTQL counseling call
 
• Describe medication regimen
 
• Describe assessment schedule
 
• Describe incentives schedule, if applicable
 
• Ask patients if want information about how to enroll in SmokefreeTXT, if applicable
 
	WTQL
Welcome Mailing (Attach- ments B- D)	
 
• Medication (sent in a separate package to those medically eligible)
 
• Medication instructions, if applicable
 
• Target quit date & follow-up reminders
 
• Contact information for WTQL & UW-CTRI (to reduce call rejection)
 
• Incentive reminders, if applicable
 
• SmokefreeTXT description, terms of use & privacy policy, if applicable
 
• Study information sheet containing all required elements of consent and HIPAA authorization
 
	WTQL
12-Week Follow Up (Attach- ment G)	
 
• Self-reported tobacco use & costs in past 7 days & since target quit date
 
• Treatment use, adherence, satisfaction, & costs
 
• Candidate mediators (perceived Quit Coach support; reduction in exposure to smoking/triggers; quitting motivation & confidence)
 
	UW- CTRI

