## Treatment procedures description

The WTQL offers a standard, evidence-based protocol comprising a single 20-minute counseling call (plus *ad hoc* calls as initiated by the participant) and a two-week supply of an over-the-counter nicotine replacement therapy. This will be the treatment that all study enrollees will receive in the 2.5-18 months preceding study enrollment and will be the base treatment in the second round of intervention to be evaluated in terms of reach, efficacy, and cost-effectiveness in the proposed study. Four interventions will be evaluated in a fully crossed design:

- Augmented counseling (4 proactive, scheduled telephone counseling sessions with a quit coach rather than the usual-care 1 call). The content of this counseling will follow existing, evidence-based protocols used by the WTQL in states that contract for this more intensive service.
- Augmented nicotine replacement therapy (4 weeks of nicotine patch plus nicotine mini-lozenge rather than the usual-care two-week supply of nicotine patch therapy), for those meeting WTQL NRT eligibility criteria. These FDA-approved, over-the-counter medications will be dispensed with instructions to use that follow package insert specifications (e.g., using lower, 2-mg dose mini-lozenges for individuals who do not smoke within 30 minutes of waking; dispensing lower, 14-mg dose patches to individuals who smoke fewer than 10 cigarettes per day), in accordance with current WTQL practice and documentation.
- Adjunctive SmokefreeTXT support (proactive enrollment in this 6-8-week text message-based cessation support program versus none). This national program is offered at no cost to users (apart from data/minute costs charged by cellular providers about which enrollees are advised at enrollment) and is sponsored by the National Cancer Institute. This program sends up to 5 messages per day for up to 2 weeks prior to the target quit day and 6 weeks following the target quit day (total duration may be longer if participants elect to change the target quit day). The text messages offer tips to help enrollees achieve their goal of quitting smoking and offer real-time interactive tips when participants text in responses indicating cravings, negative moods, or slips. Participants have the option to reset quit dates and have the option to unsubscribe at any time by texting STOP to the program.

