## **Data Safety and Monitoring Plan**

The Data Safety and Monitoring Plan (DSMP) for this research comprises not only the research conducted directly by the University of Wisconsin Center for Tobacco Research and Intervention (UW-CTRI) researchers, but also research conducted by other investigators collaborating with UW-CTRI-funded projects. All investigators must agree to comply with the procedures outlined in this DSMP. This DSMP does not reduce any investigator's obligation to comply with the requirements of the Institutional Review Board (IRB) at his/her home institution or the IRB of any collaborating organizations.

*Monitoring the progress of trials and the safety of participants.* The Principal Investigators (PIs) are responsible for routine monitoring of study progress. This includes scheduled meetings with study staff at least monthly; review of weekly reports from the Wisconsin Tobacco Quitline (WTQL) vendor, Optum, whose personnel will recruit, screen, enroll, counsel, and compensate participants for treatment engagement; and review of monthly reports of use of SmokefreeTXT. Weekly reviews of WTQL reports and follow-up discussions as needed to address any concerns with Optum are vital as the study procedures, database queries, and reports are being developed,

launched, and refined in the first year of the project. Following roll-out, monthly review meetings will continue to monitor progress and to consider up- or down-regulating the rate of recruitment from month to month. Data reviewed at these meetings will include the number and type of participants enrolled, the number and reasons for exclusions from enrollment, the number of counseling sessions completed, the number of SmokefreeTXT enrollees who opt-out, and the timeliness and accuracy of incentive payments to participants. Adverse or unanticipated events reported at WTQL counseling calls will be addressed using standard WTQL protocols to address medication side effects, withdrawal, or other concerns. The DSMC will review reports on adverse events reported to the WTQL. Adverse or unanticipated events (e.g., failure to receive an earned incentive) reported by participants directly to UW-CTRI through proactive participant calls (participants will receive this contact information at enrollment) will be reported to Optum to record and attempt to resolve the event, and will be reported to the IRB, FDA, or NCI, as appropriate based on the severity and protocol relevance of the event.

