To facilitate participant safety, study participants must meet study inclusion and exclusion criteria. Once enrolled, WTQL protocols will assess NRT eligibility and the presence of AEs and SAEs during treatment. Should either excessive risk to study participants and/or convincing evidence of lack of measurable benefit to study participants be determined, the study will be stopped and all participants notified in a manner appropriate to the nature of the risk and/or lack of benefit. When taking that step, the investigators will consult with the IRB and NCI.

Plans for assuring compliance with requirements regarding the reporting of adverse events. This DSMP requires that investigators notify NIH and the University of Wisconsin IRB in a timely manner (consistent with IRB and NIH policies) of the occurrence of any SAE or any AE which is severe, unexpected, and possibly related to study medication or protocol. Because this study involves pharmaceutical agents, if an unexpected SAE might be related to study drug use, both the Food and Drug Administration (FDA) and the manufacturer will also be notified within 5 days of investigators becoming aware of the event. Examples of unexpected SAEs would be untoward medical or intervention occurrences that result in death, are life-threatening, require hospitalization or prolonging of existing hospitalization, create persistent or significant disability/incapacity, or involve congenital abnormality/birth defects. Unanticipated AEs include less serious problems that merit reporting to the DSMC because they are severe, unexpected, and possibly related to study participation. Any SAE will be queried and reported even if it appears that the serious adverse event is unrelated to study participation. Because the interventions will be delivered by our WTQL partner, Optum, staff there will be responsible for assessing and managing any adverse events related to study medication in accordance with their existing protocols for monitoring NRT medication side effects or unanticipated health events during counseling calls. The study team will review Optum reports of unanticipated health events no less than bi-weekly, and Optum will notify the PIs of any severe, unanticipated, and possibly study-related adverse events in a timely manner so that NIH, FDA, and the IRB may be notified, as needed.

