Data and Safety Monitoring Committee. In addition to the protections outlined in the DSMP (above), all research activities conforming to the NIH definition of a clinical trial will also have an independent Data Safety and Monitoring Committee (DSMC). This application includes a Phase IV clinical trial using FDA-approved medications. The DSMP specifies overall monitoring that will be conducted by Optum, as the intervention deliverer, and by the PIs, including timely reporting of AEs and SAEs. Every six months, the DSMC will convene to review the overall safety data, as well as data on safety summarized by treatment condition. As per NIH guidelines, the objective of these reviews will be to determine whether continued conduct of the trial poses any undue risk for participants.

The existing UW-CTRI DSMC is chaired by [name], leader of the Cancer Control Program of the UW Comprehensive Cancer Center. [name] is an experienced physician and clinical trial researcher with no involvement in any of this project's research activities. [name] is joined on the DSMC by [name] and [name]. [name] is Associate Professor of Medicine and Medical Director of the HIV/AIDS Comprehensive Care Program at UW Hospital and Clinics who has previously collaborated on a clinical trial of smoking cessation with

UW-CTRI. [name] is an otolaryngologist who has served on independent DSMBCs for Phase II and III trials involving a nicotine vaccine. Neither has direct involvement with any of the proposed research. The PIs will report to the DSMC; the three DSMC members will be unblinded as to treatment conditions and will make the final determinations as to study continuation.

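### Adverse events are described as asked about on counseling calls, whose number is randomized 1 vs 4; unless unseen forms ask all arms equally, the DSMC's by-condition counts are not like-for-like on the counseling factor

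*Combined protocol and SAP*

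**What the plan says.** Section G (Detailed study procedures) gives AE assessment to the treatment provider: "Staff at the WTQL will also be responsible for assessing adverse events related to its interventions in accordance with their existing protocols". The Data Safety and Monitoring Plan places that activity on the calls, referring to the vendor's "existing protocols for monitoring NRT medication side effects or unanticipated health events during counseling calls".

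The number of calls is a randomized factor. The table in Section II (Goals/Aims) lists "1 vs. 4 proactive counseling calls", and the Treatment procedures description specifies "4 proactive, scheduled telephone counseling sessions with a quit coach rather than the usual-care 1 call". In the Schedule of Study Activities, staff "Schedule first/only WTQL counseling call" at treatment initiation; the timing of that call relative to NRT use is not given.

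On review, the monitoring plan says "The DSMC will review reports on adverse events reported to the WTQL". At its six-monthly meetings the committee sees overall safety data "as well as data on safety summarized by treatment condition". The plan adds that "the three DSMC members will be unblinded as to treatment conditions".

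Other routes exist. Every participant may request extra coaching (Sections D and H) and may call UW-CTRI directly (monitoring plan). Section H mentions routine vendor monitoring, and the monitoring plan mentions standardized assessments, but neither gives a schedule by arm. The content listed for the 12- and 26-week interviews (Assessment Plan item 4 and the Schedule of Study Activities) contains no AE item. The Aim 2 analysis plan says health care utilization is collected at follow-up, for the cost analysis; no text sends those answers to the DSMC.

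**The concern.** The one setting the plan names for AE enquiry occurs four times as often, by schedule, in half of the cells as in the other half, and safety is tabulated by cell. More occasions to be asked means more chances for the same event to be recorded. A difference between counseling levels in the DSMC tables could then reflect contact rather than harm, and nothing in the plan says the committee receives the information needed to tell these apart. It knows the assigned number of calls, but completed sessions are listed only among the data reviewed at the investigators' progress meetings, and the source of each report is not mentioned.

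At stake is the interpretation of the by-condition safety tables on one factor, and to some degree how fully events are captured where only one call is scheduled. Abstinence outcomes come from follow-up interviews by staff blind to condition and are not touched.

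**Working it through.** The documents give no AE rate, capture rate or call-completion rate, so there is no figure of the plan's own to reproduce. Only the ratio of scheduled occasions follows from the text.

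**Scheduled occasions.** Eight of the 16 cells have one call and eight have four. With equal cells (an assumption) and N = 1,408 there are 704 participants per level: 704 × 1 = 704 scheduled calls against 704 × 4 = 2,816. With N = 1,600 the figures are 800 and 3,200. The ratio is 4:1.

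**Recorded ratio: illustration on assumed inputs.** True risk is equal in all arms. Let c be the share of scheduled calls completed, q the chance that a completed call captures a given event, u the share of events reported outside scheduled calls (same in all arms), and k the number of scheduled calls. Captures are taken as independent.

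Recorded share = 1 − (1 − u)(1 − cq)^k. The recorded ratio is the share at k = 4 divided by the share at k = 1.

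Worked case, c = 0.60, q = 0.20, u = 0.20, so cq = 0.12:
- one call: 1 − 0.80 × 0.88 = 0.296
- four calls: 1 − 0.80 × 0.88^4 = 0.520
- ratio: 0.520 / 0.296 = 1.76

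Ratios at c = 0.60:

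| u | q = 5% | q = 10% | q = 20% | q = 50% |
|---|---|---|---|---|
| 20% | 1.30 | 1.51 | 1.76 | 1.84 |
| 40% | 1.12 | 1.22 | 1.36 | 1.48 |
| 60% | 1.06 | 1.10 | 1.17 | 1.26 |
| 80% | 1.02 | 1.04 | 1.07 | 1.11 |
| 90% | 1.01 | 1.02 | 1.03 | 1.05 |

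With all calls completed (c = 1), the ratios across the four q values are 1.45 / 1.70 / 1.87 / 1.58 at u = 20% and 1.19 / 1.32 / 1.45 / 1.38 at u = 40%.

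**In counts.** With 704 per level, an assumed 10% true event rate, c = 0.60 and q = 0.20, the expected recorded events are 70.4 × share: about 21 vs 37 at u = 20%, 33 vs 45 at u = 40%, and 64 vs 66 at u = 90%.

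**Direction.** If 1-call participants use other routes twice as much (u = 40% against 20% in 4-call participants, c = 1), the ratio is 0.81 / 1.03 / 1.29 / 1.36. A higher count with four calls is therefore a tendency, not a certainty. Call timing is not modelled and could move the ratio either way.

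**Correlated reporting.** If willingness to report varies between people (intraclass correlation 0.5, same mean q, c = 1), the ratios shrink to 1.17-1.36 at u = 20% and 1.07-1.19 at u = 40%.

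**NRT comparison.** NRT is fully crossed with counseling, so each NRT level contains the same mix of 1-call and 4-call cells. If capture is the same at both NRT levels, the marginal ratio is undistorted. If capture per call is 25% lower (relative) in the combination cells, a true ratio of 1.5 appears as 1.31-1.45; if 25% higher, as 1.55-1.67 (c = 1, u = 20-40%).

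**The case against.** The strongest reply is that the deciding documents are not available. The vendor's AE protocol and the follow-up form (Attachment G) could already ask every arm the same questions at the same times. The monitoring plan also says AEs and SAEs are assessed during treatment, without limiting this to scheduled calls, and promises standardized assessments involving the study team. This stands as a limit: unequal ascertainment is what the text describes, not something shown to have happened. It does not dispose of the point, because a standard question asked four times still yields more than the same question asked once, and no passage says the arms are asked equally often.

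Second, severe events and SAEs, which the monitoring plan stresses, are likely to be volunteered whatever the call schedule. Study staff review vendor reports at least bi-weekly, the investigators carry responsibility for SAE detection, and events told to UW-CTRI are passed to the vendor to record. This also stands. It is why the table runs to u = 90%, where the ratio is at most 1.05.

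Third, an unblinded committee would readily think of extra contact as an explanation. That is fair, but assigned call number alone does not show how many calls took place or where each report came from.

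A reader might infer that recorded AEs would differ three- or fourfold. Ratios of 2.95-3.88 arise only with low capture per call (2-20%), all four calls completed and no reporting outside them, which contradicts the routes open to every arm.

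**Conclusion.** The point holds in conditional form. As described, AE enquiry is tied to a randomized factor, so by-condition AE counts are not like-for-like on counseling unless the unseen vendor protocol or follow-up form equalizes the enquiry. Counts will tend to be higher with four calls at equal true risk. On the stated assumptions (60% completion, 5-50% capture per call, 20-90% reported elsewhere) the ratio lies between about 1.8 and about 1.0, and it can drop below 1 if 1-call participants rely more on other routes. The effect is probably smallest for severe events and SAEs.

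Three stronger readings are tempting but unsupported. One is that the NRT safety comparison is biased: crossing protects its margin if capture is equal at both NRT levels. Another is that an arm could be wrongly dropped: the only stopping action given concerns the whole study, and no arm-dropping rule is stated. The third is that events in the cells pairing one call with 4-week patch plus lozenge (cells 5-8; 4 × 88 = 352 of 1,408, or 4 × 100 = 400 of 1,600, if medically eligible) will go undetected: any low capture there comes from assumed inputs, not from the documents.

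No efficacy aim is affected. This is a minor improvement to safety monitoring.

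**What to change.** Main change, in three parts:
- In the DSMC's by-condition tables, show completed calls (scheduled and on-request) and the source of each report beside the AE counts.
- Compare NRT levels within counseling level or on the factor margin, not across cells with different call numbers.
- State in the monitoring plan on which calls AEs are asked about.

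The cost is a table-format change, a sentence of protocol text and one transfer of call counts. The investigators already review completed counseling sessions.

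Optional: if Attachment G or the health care utilization items already ask all arms about hospitalization or health events, name those items and send the answers to the DSMC as a supplementary source. Give response rates by condition, since Section B itself anticipates attrition where incentives are absent or minimal. Someone other than the blinded interviewers would have to link answers to condition.

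Adding new AE questions to the interviews is a larger step. The windows are 11-18 and 25-38 weeks after the quit day, while NRT is supplied for 2-4 weeks, so recall of side effects would be weak. The monitoring plan also requires every SAE to be queried and reported even if it appears unrelated, so each positive answer could add work. The sponsor should weigh that burden; the main change does not depend on it. Call-based and participant-initiated reporting stay as they are.
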